Abbreviations: AE = adverse event; BMI = body mass index; ECG = electrocardiogram; HbA1c = hemoglobin A1c; no. = number; VAS = visual analog scale.

Table 2 Assessment Schedule for Visit 2 (Part A)

Approx. hour	Nominal timing	Activity	Other
Day -1		Participant arrives after dinner for overnight stay at the trial site and continued eligibility will be checked. The participant will continue personal diabetes management care. Participants will be instructed to avoid the use of the central abdominal area for their personal infusion set (for at least 3 days) prior to arrival at the CRU and continue insulin infusion with their personal insulin pump.	SARS-CoV-2 test may be performed according to the site general procedures AEs, concomitant medication, alcohol breath test, vital signs, urine pregnancy test
Day 1		Breakfast	
		Measure and record adipose thickness by ultrasound at infusion sites Collect image of each local infusion site prior to insertion of the corresponding infusion set using CCI Platform	These measurements may be performed at any time after the subject's arrival on Day -1 until infusion set insertion. Each local infusion site should be labeled and have a unique identifier for CCI Platform image acquisition
		Study pumps loaded with study treatment	
+0 h		Insert infusion set cannula into infusion site 1 and start pump at a basal rate of 1 U/h	
+0.5 h (± 5 min)		Insert infusion set into infusion site 2 and start pump at a basal rate of 1 U/h	
+1 h (± 5 min)		Insert infusion set into infusion site 3 and start pump at a basal rate of 1 U/h	
+1.5 h (± 5 min)		Insert infusion set into infusion site 4 and start pump at a basal rate of 1 U/h	
+2.0 h (± 5 min)		Insert infusion set into infusion site 5 and start pump at a basal rate of 1 U/h	
+3.0 h (± 3 min)	-5 min ^b	Collect VAS score for infusion site 1	
	0 min	Administer 15 U bolus to infusion site 1 at quick bolus speed (15 U/min)	
	+1 min ^a	Collect VAS score for infusion site 1	
	+15 min ^b	Collect VAS score for infusion site 1	
+3.5 h (± 3 min)	-5 min ^b	Collect VAS score for infusion site 2	

Approx. hour	Nominal timing	Activity	Other
	0 min	Administer 15 U bolus to infusion site 2 at quick bolus speed (15 U/min)	
	+1 min ^a	Collect VAS score for infusion site 2	
	+15 min ^b	Collect VAS score for infusion site 2	
+4.0 h (± 3 min)	-5 min ^b	Collect VAS score for infusion site 3	
	0 min	Administer 15 U bolus to infusion site 3 at quick bolus speed (15 U/min)	

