	0 min	Administer 15 U bolus to infusion site 3 at quick bolus speed (15 U/min)	
	+1 min ^a	Collect VAS score for infusion site 3	
	+15 min ^b	Collect VAS score for infusion site 3	
+10.5 h (± 3 min)	-5 min ^b	Collect VAS score for infusion site 4	
	0 min	Administer 15 U bolus to infusion site 4 at quick bolus speed (15 U/min)	
	+1 min ^a	Collect VAS score for infusion site 4	
	+15 min ^b	Collect VAS score for infusion site 4	
+11.0 h (± 3 min)	-5 min ^b	Collect VAS score for infusion site 5	
	0 min	Administer 15 U bolus to infusion site 5 at quick bolus speed (15 U/min)	
	+1 min ^a	Collect VAS score for infusion site 5	
	+15 min ^b	Collect VAS score for infusion site 5	

Approx. hour	Nominal timing	Activity	Other
+11.5 h (± 3 min)		Remove infusion sets, evaluate local infusion sites Collect image of each local infusion site after removal of the corresponding infusion set using CCI Platform	Each local infusion site should be labeled and have a unique identifier for CCI Platform image acquisition that is the same as prior to infusion
+12.5 h (± 30 min)		Participant discharge from CRU	Following the final evaluation, the participants will have the option to spend the night or be discharged from the CRU

[figure not shown]
Abbreviations: AE = adverse event; Approx. = approximately; CRU = clinical research unit; SARS-CoV-2 = severe acute respiratory syndrome coronavirus 2; VAS = visual analog scale.

- a The VAS time point of 1- minute (+1 min) is to be collected from the start of bolus infusion.
- b The VAS time points of -5 (± 2 min), and 15 (± 2 min) minutes are to be collected from start of bolus infusion.

CCI

CCI

CCI

2. Introduction

LY900014 (Lyumjev®) is an ultra-rapid-acting formulation of insulin lispro for subcutaneous (SC) and intravenous use that employs excipients, citrate and treprostinil, to accelerate time action, along with magnesium to enhance insulin stability, resulting in improved glycemic control in participants with type 1 diabetes mellitus (T1D) or type 2 diabetes mellitus.

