2.3. Benefit/Risk Assessment

There is no direct clinical benefit anticipated from participation in this trial.

The treatments (sodium citrate, magnesium chloride, Humalog diluent, or treprostinil) within this study are administered below approved therapeutic levels and are considered placebo treatments. No known potential risks are associated with the use of small amounts of treprostinil, sodium citrate, magnesium chloride, or Humalog diluent. Furthermore, these study treatments are well characterized, and the description of each treatment relative to a therapeutic use is described in Section 8.4.

Potential risks associated with CSII pump use

- Minor skin irritation, sensitization, or localized inflammatory response can occur if skin contacts bioincompatible materials.
- Pain, bruising, swelling, redness, and bleeding at the infusion set insertion site.

The occurrence and severity of these events are not expected to be different from routine use of the Medtronic™ MiniMed™ 770G pump. More detailed information about the known and expected risks and potential adverse events may be found in the manufacturer's instructions.

3. Objectives and Endpoints

Objectives	Endpoints
Part A	
Primary	
To investigate local infusion site pain for infusions of sodium citrate and treprostinil in Humalog diluent with magnesium chloride (without insulin) in the abdominal, arm, thigh, and buttock areas in participants with T1D on CSII.	VAS pain score
Secondary	
To investigate local infusion site pain of 2 different cannula insertion depths (6 mm and 9 mm) in participants with T1D on CSII	VAS pain score
Exploratory:	
To assess local infusion site reactions using the exploratory CCI Platform	Characterization and measurement of incidence and severity of local infusion site reaction data

Abbreviations: CSII = continuous subcutaneous insulin infusion; VAS = visual analog scale; T1D = type 1 diabetes mellitus.

4. Study Design

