6.1.1. Administration Details

[figure not shown]
Study treatment will be administered via CSII at a basal infusion rate of 1 U/hr and 15 U bolus doses will be delivered at quick bolus speed (15 U/min) per the SoA (Section 1.3). Medtronic™ MiniMed™ 770G pumps will be used in manual mode for infusion of all study treatments. The

pump requires 1 new AA (1.5 V) battery. For best results, use a new AA lithium (FR6) battery. The pump also accepts an AA alkaline (LR6). MiniMed™ 3-mL reservoirs and MiniMed™ Mio™ Advance infusion sets will be used with the pumps.

Pumps will be programmed with the following settings:

- Preferred language
- Current date and time
- Single basal pattern of 1 U/hr with start time 12:00AM and end time 12:00AM
- Bolus increment of 0.1 U
- Bolus speed quick (15 U/min)
- Bolus type normal
- Bolus entry method manual

In Part A, 5 pumps will be used for each participant. For each pump, a 3-mL reservoir will be filled by a qualified site staff member with 3 mL of study treatment, a MiniMed™ Mio™ Advance infusion set will be attached to the filled reservoir and the reservoir will be loaded into the pump. The infusion set tubing will be primed, and a cannula fill with 0.6 unit for both 6 mm and 9 mm cannula will be completed. Six mm cannula will be inserted into each of the designated areas (abdomen, arm, thigh, and buttock), avoiding any areas of lipohypertrophy or surgical scars. At the abdominal area only, 9 mm cannula will be used in addition to the 6 mm cannula. In case of immediate infusion set intolerance or insulin flow block alarm occurs, a new infusion set can be inserted within the first 10 minutes of initiation of the infusion site. **CCI**

Appropriately trained staff must be available until the participants complete the infusions. The pump can be reused after disinfection, according to the local procedure.

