8.4. Treatment of Overdose

There is a low risk of an overdose from either sodium citrate, magnesium chloride, Humalog diluent or treprostinil within this study.

The largest planned total dose of study treatment will be administered in Part A of the study when each participant will have 5 pumps and will receive a total dose of 270 U/day. The total amount of study treatment (sodium citrate, magnesium chloride, Humalog diluent or treprostinil) provided would be comparable to Humalog or Lyumjev administration to individuals with diabetes who are highly-insulin resistant and require more than 200 U of insulin per day.

Likewise, Reznik (2010) reviewed the data from 4 patients with type 2 diabetes with insulin resistance who were placed on CSII therapy with a concentrated insulin to address their daily insulin requirements (192U-630U). Although rare, patients with extreme insulin resistance requiring 10,000 U of insulin per day have been reported (Lalej-Bennis et al. 1997).

Additionally, the total dose for each study treatment is well below any therapeutic level:

- Sodium citrate as it is listed in the FDA Generally Recognized as Safe (FDA 2015a) food additives database and total amount given (11.9 mg as trisodium citrate dihydrate) is within the limits identified for approved drug products in the FDA Inactive Ingredients in Approved Drugs database (FDA 2015b).
- Magnesium chloride is a cation primarily intracellular. The total planned dose in Part A is 13.5 μ mol magnesium (or 2.74 mg magnesium chloride hexahydrate) and is below the therapeutic use (Lavoisier magnesium chloride 2004):

Therapeutic Indication	Administration
Curative treatment of torsades de pointe (TdP)	Intravenous bolus in 8 mmol of magnesium cation
Treatment of acute hypokalemia associated with hypomagnesemia	Intravenous infusion from 24 to 32 mmol of magnesium cation daily
Magnesium supplement during electrolyte rebalance and parenteral nutrition	Intravenous infusion from 6 to 8 mmol of magnesium cation over 24 hours
Preventive and curative treatment of eclampsia crisis	Intravenous infusion of 16 mmol of magnesium cation, i.e. 3.5 g of magnesium chloride for 20 to 30 minutes.

Based on the drug label (Lavoisier magnesium chloride 2004), the first signs of overdose of hypermagnesemia include inhibition of knee jerks, feeling of heat, drowsiness, spoken speech disorders, muscular paralysis with respiratory disorders and at the most, respiratory and cardiac arrest.

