- Treprostinil is approved in many European Member States for use in the treatment of pulmonary arterial hypertension (PAH) and is known as Remodulin® for SC administration (Remodulin SPC 2016). In Part A, participants will be administered a planned total dose of treprostinil of 2700 ng. The maximum total daily dose of treprostinil in the study will be a small fraction of the average Remodulin® therapeutic dose (53- to 1707-fold less; [Table 7](#)). Based on the drug label, the signs and symptoms of overdose with Remodulin® during clinical trials are extensions of its dose-limiting pharmacologic effects and include flushing, headache, hypotension, nausea, vomiting, and diarrhea. Most events were self-limiting and resolved with reduction or withholding of Remodulin®.

Table 7 Maximum Estimated Treprostinil Dose in Diabetes Relative to Treprostinil Doses for Pulmonary Arterial Hypertension

Treprostinil Therapeutic Indication	Treprostinil Dose		Treprostinil dose in PAH patients vs Treprostinil Dose in study ^b
	ng/kg/min	ng/kg/day	
Total Dose in Part A			
• Maximum dose ^a	-	33.75	-
PAH (Remodulin®)^c			
• Lowest starting dose	1.25	1800	53-fold
• Average dose	9.3	13392	397-fold
• High dose	40	57600	1707-fold

Abbreviations: PAH = pulmonary arterial hypertension.

a Total Treprostinil dose in Part A (2700ng/80kg) assuming 80 kg body weight for an adult with T1DM

b Treprostinil dose in study vs PAH patients = treprostinil dose for PAH ÷ maximum treprostinil dose in study (Part A)

c Remodulin SPC 2016.

The sponsor does not recommend specific treatment for an overdose.

In the event of an overdose, the investigator/treating physician should:

1. Turn off all study pumps immediately.
2. Contact the medical monitor immediately.
3. Closely monitor the participant for any AE/SAE until study infusion no longer has a clinical effect or at least until the end of each visit. Refer to Section 10.3 Appendix 3 for reporting details.
4. Document the quantity of the excess dose, as well as the duration of the overdose, in the CRF.

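### Does the planned Part A total of 270 U in Protocol Section 8.4 understate what Table 2 schedules?

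*Protocol*

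**What the plan says.** Section 8.4 (Treatment of Overdose) gives the largest planned exposure as the Part A day, when "each participant will have 5 pumps and will receive a total dose of 270 U/day". It then states amounts for that day: 11.9 mg citrate, 13.5 µmol magnesium (2.74 mg as the hexahydrate), and for treprostinil "participants will be administered a planned total dose of treprostinil of 2700 ng". Table 7 divides the treprostinil amount by a body weight, "assuming 80 kg body weight for an adult with T1DM", to get 33.75 ng/kg/day. It sets this against three doses used in pulmonary arterial hypertension, with ratios of 53 (lowest starting dose), 397 (average dose) and 1707 (high dose). The sentence introducing the table reads "The maximum total daily dose of treprostinil in the study will be a small fraction of the average" Remodulin therapeutic dose, and gives the range 53- to 1707-fold.

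The benefit/risk section relies on this material: "the description of each treatment relative to a therapeutic use is described in Section 8.4".

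Table 2 in Section 1.3 starts the five basal infusions half an hour apart. The last, at +2.0 h, reads "Insert infusion set into infusion site 5 and start pump at a basal rate of 1 U/h". Each site gets its third bolus 9 h after its own start (+9.0 to +11.0 h). One row at +11.5 h then covers all sites: "Remove infusion sets, evaluate local infusion sites". Section 6.1.1 programs the pump with "Single basal pattern of 1 U/hr with start time 12:00AM and end time 12:00AM".

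**The concern.** The 270 U leaves room for exactly 9 h of basal at each site. On its face Table 2 has every pump attached for longer than that, from 9.5 h at the fifth site to 11.5 h at the first, with a pump pattern that does not switch itself off. A participant treated exactly to schedule would then receive more than the amount the protocol describes as the largest planned and, in Table 7, as the maximum. Every excipient total and margin in Section 8.4 would be wrong in the same proportion. A safety comparison that the benefit/risk section points to should agree with the protocol's own schedule.

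Two wording points sit beside it. The 53- to 1707-fold range is attached to the average therapeutic dose, while Table 7 assigns those two ends to the lowest starting dose and the high dose. And the row labelled as a maximum is a value at one assumed body weight.

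**Working it through.** **Inputs.** Five pumps (Section 4.1); three 15 U boluses per site and 1 U/h basal (Table 6); basal starts at +0, +0.5, +1.0, +1.5 and +2.0 h and removal at +11.5 h (Table 2); 1 U = 10 µL (Synopsis); 15 mM citrate, 5 mM magnesium chloride and 1 µg/mL treprostinil (Table 6); 0.6 U cannula fill per site (Section 6.1.1).

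**Reproducing the stated figures.**
- Bolus: 5 × 3 × 15 = 225 U.
- Basal implied by 270 U: (270 − 225) / 5 = 9.0 h per site, the interval from each site's start to its third bolus.
- Volume: 270 × 10 µL = 2.70 mL.
- Treprostinil: 2.70 mL × 1000 ng/mL = 2700 ng; 2700 / 80 = 33.75 ng/kg.
- Magnesium: 2.70 mL × 5 mM = 13.5 µmol. Citrate: 2.70 mL × 15 mM = 40.5 µmol. With molar masses of 203.30 and 294.10 g/mol (my assumption; the documents give none) these are 2.74 mg and 11.9 mg, as stated.
- Margins: 1800 / 33.75 = 53.3; 13392 / 33.75 = 396.8; 57600 / 33.75 = 1706.7.

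Section 8.4 is therefore internally consistent. The only question is the 9 h.

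**Basal to set removal.**
- Hours: 11.5 + 11.0 + 10.5 + 10.0 + 9.5 = 52.5 h, so 52.5 U.
- Total: 225 + 52.5 = 277.5 U; 277.5 / 270 = 1.028.
- The extra 7.5 U is the basal between third bolus and removal: 2.5 + 2.0 + 1.5 + 1.0 + 0.5 h.
- Windows: four starts at ±5 min and five sites with removal at ±3 min give ±(20 + 15)/60 = ±0.58 U, so 276.9 to 278.1 U.

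**Range over what the protocol leaves open.**

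| Basal stops at | Total (U) | Against 270 U |
|---|---|---|
| Third bolus | 270 | 0 |
| The +15 min rating: 225 + 5 × 9.25 | 271.25 | +0.5% |
| Set removal | 277.5 | +2.8% |
| Set removal, cannula fill counted: + 5 × 0.6 | 280.5 | +3.9% |

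**Effect at 277.5 U (2.775 mL).**
- Treprostinil 2775 ng; 2775 / 80 = 34.69 ng/kg; margins 1800, 13392 and 57600 over 34.69 = 51.9, 386.1 and 1660.5.
- Magnesium 13.875 µmol (2.82 mg); citrate 12.2 mg.
- Smallest magnesium use listed in Section 8.4: 6 mmol / 13.875 µmol = 432-fold, against 6 mmol / 13.5 µmol = 444-fold.

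**An outer bound.** Each reservoir holds 3 mL. If all five were emptied, 15 mL would give 15,000 ng treprostinil, or 187.5 ng/kg at 80 kg, still 1800 / 187.5 = 9.6-fold below the lowest starting dose. No reading of the basal duration comes near that.

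**Effect on the analysis.** The ratings at a site are taken around boluses nominally 3, 6 and 9 h after that site's own start, so each has the same scheduled basal time behind it at every site. Beyond the +15 min rating, the basal tail after the third bolus comes after the last pain score. Its length depends on position in the order and not on location, and the Latin square in Table 4 balances position across locations. The mixed model in SAP Section 9.3.1 has no term for total dose.

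**The case for a change.** The best case for acting is that the mismatch is real on the natural reading and cheap to correct. Section 4.1 goes from the third bolus to the pain ratings and then to removal of sets and pumps, with no step that stops the basal. The pump pattern runs round the clock. The timing windows cannot absorb 7.5 U. Section 8.4 also asks the site to record the size of any excess dose, which presupposes a planned amount that matches the schedule.

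Most of that stands as description. Less of it stands as a reason to amend. Continuation to removal is an inference: no visible passage gives a stop time, text near the pump instructions is blacked out, and 270 U is exact if basal ends at each third bolus. The total of 277.5 U is not the only alternative either, because the cannula fill is left out of both figures. Section 8.4 sets no numeric overdose threshold at 270 U, and Section 6.4 has infusion times and start and stop dates recorded, so the amount actually given can be worked out from the record.

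Of the wording points, the sentence on the average dose is a genuine slip, but it cites Table 7 in the same parenthesis and the table assigns the three ratios correctly. The label on the 33.75 ng/kg row is answered by the table's own footnotes: footnote b ties the maximum to Part A, and footnote a discloses the 80 kg. Body weight matters more than the basal tail: at an assumed 60 kg, 2700 ng is 45 ng/kg, or 40-fold. That assumption is open to the reader; it is not an error.

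**Conclusion.** The arithmetic behind the concern is right, but no change to the plan follows. The 270 U counts 9 h of basal per site. If basal runs to set removal the total is 277.5 U (+2.8%), or 280.5 U (+3.9%) with the cannula fill counted as dose. The lowest treprostinil margin moves from about 53-fold to about 52-fold. Section 8.4 is an order-of-magnitude comparison of planned, estimated amounts with therapeutic use, and it reaches the same conclusion at any of these totals. Its comparison with people who need more than 200 U of insulin a day is also unaffected.

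This rests on the 1 U/h rate and Table 2 times as printed, on the 80 kg that Table 7 assumes, and on nothing in the blacked-out text changing the basal duration. Section 8.4, Table 7, Table 2 and Section 6.1.1 should be made to agree on that duration, and the sentence on the average dose corrected, when the document is next revised for another reason. Both are clerical and alter nothing that the trial measures, analyses or concludes.

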8.5. Pharmacokinetics

Pharmacokinetic parameters are not evaluated in this study.

8.6. Pharmacodynamics

Pharmacodynamic parameters are not evaluated in this study.

8.7. Genetics

Genetics are not evaluated in this study.

8.8. Biomarkers

Biomarkers are not evaluated in this study.

8.9. Immunogenicity Assessments

Immunogenicity assessments are not evaluated in this study.

8.10. Medical Resource Utilization and Health Economics

Medical resource utilization and health economics are not evaluated in this study.

9. Statistical Considerations

9.1. Statistical Hypotheses

The hypotheses being tested are as follows:

- Part A: To test for differences between infusion sites and depth of infusion in pain as measured by the VAS pain score.
- CCI
[REDACTED]

9.2. Analyses Sets

The following analysis sets are defined:

Participant Analysis Set	Description
Full analysis set	All randomized participants. Participants will be included in the analyses according to the randomly assigned sequences.
Safety analysis set	All randomized participants who receive at least 1 infusion. Participants will be analyzed according to the infusions they actually received.

Data related to a site where an infusion set cannula is accidentally pulled out of an infusion site will not be used in the analysis.

9.3. Statistical Analyses

Statistical analysis of this study will be the responsibility of Lilly or its designee.

Any change to the data analysis methods described in the protocol will require an amendment only if it changes a principal feature of the protocol. Any other change to the data analysis methods described in the protocol, and the justification for making the change, will be described in the statistical analysis plan (SAP) and the clinical study report. Additional exploratory analyses of the data will be conducted as deemed appropriate.

9.3.1. General Considerations

Unless otherwise specified, these general considerations will apply to all analyses. Continuous variables will be summarized by the number of observations, mean, standard deviation, minimum, median, and maximum values. Categorical variables will be summarized by counts and percentages. Summaries will be provided by infusion site locations, including cannula depths, and study treatments (excipients).

9.3.2. Primary Endpoints

Infusion site pain assessed using the VAS pain score will be listed and summarized using standard descriptive statistics by bolus time (3, 6, and 9 hours after initiation of basal infusion) and VAS assessment time point (5 minutes prior to bolus and 1 and 15 minutes after bolus). For Part A, the summary will also be by infusion site location. The 5 infusion site locations include the assessment of 2 cannula depths at the abdominal site. CCI
[REDACTED]

CCI

A mixed effects model will be used to analyze from the log transformed VAS pain score for each bolus time and VAS time point. The statistical model for Part A will include terms for infusion site location, period (order of infusions), bolus time, VAS time point, the 2- and 3-way interactions between infusion site location, bolus time, and VAS time point as fixed effects and participant as a random effect. Comparisons will be made between infusion site locations and between cannula insertion depths for the abdominal infusion site for each bolus time and VAS time point. **CCI**

Least-squares means (LSMeans), infusion site location/treatment differences in LSMeans, and the corresponding 95% confidence intervals (CIs) for the infusion site location/treatment differences will be estimated and back-transformed from the log scale to provide estimates of the ratio of geometric LSMeans and 95% CI for the ratio of these means. It is possible that VAS scores will be 0; if so, all scores may be updated to log (VAS+1) to allow for the inclusion of the 0 values in the analysis.

The same model will also be used to analyze the change from the pre-bolus time point (5 minutes prior to the bolus) to the post-bolus time points of (1 and 15 minutes after bolus).

